13 QUALITY CONTROL AND QUALITY ASSURANCE

13.1 Site Set-up and Initiation

The Chief Investigator must sign an agreement to document the expectations of the clinical team and the sponsor – MIAT. The agreement document must be completed before participation. The Chief Investigator (CI) is required to sign a Clinical Trials Task Delegation Log, which documents the agreements between the CI and MIAT. All PIs will be asked to sign the necessary agreements, including a Site Signature & Delegation Log between the PI and MIAT, and supply a current CV and GCP certificate to the sponsor. All site staff who are performing trial-specific tasks are required to sign the Site Signature and Delegation Log, which details all functions that have been delegated to them by the PI. Prior to commencing recruitment, each recruiting site will undergo a process of initiation, either a meeting or videoconference, at which critical members of the site research team are required to attend, covering aspects of the trial design, protocol procedures, adverse event reporting, collection and reporting of data and record keeping. Sites will receive an investigator's site file, instructions, and other documentation required to conduct the trial. The sponsor must be informed immediately of any change in the site research team.

13.2 Sampling System Integrity

The device manufacturer adheres to a QC regime which includes verification, by Lot Number of: Wetreagent component concentrations, Blank test-paper colour, Accuracy of finished device on Uric Acid Standards, Reproducibility of finished device on UA Standards, with records available for inspection.

Integrity of patient/kit ID as well as resulting sampling data are assured by unique design and verification of the Device, App, and Server.

Time-stamping of photograph and then receipt by database will allow identification of diurnal variation and the subject will be automatically advised to adhere to same-time-each-day procedure.

Plausibility of each colorimetric result is controlled by the correlation of two optical parameters, saturation and luminance, in the assay algorithm. If the two results differ by a defined margin, a request for a repeat-test will be sent to the subject.

Accuracy of CRF data excerption from Patient Records will be controlled by a monthly spot-check of 10% of CRFs by a qualified independent individual from another hospital, with any required corrective action identified.

13.3 Risk Assessment

A risk assessment has been completed in line with St George's University Hospitals and Epsom and St Helier University Hospitals standards and policies. A risk management file was developed for the clinical trial to identify issues that participants and trial staff may face that might affect the study's quality. The file is available for consultancy. No unacceptable risk was identified that could compromise the physical or mental well-being of people involved in the trial.

13.4 Monitoring (onsite and central monitoring)

St George's University Hospitals and Epsom and St Helier University Hospitals Research Teams will monitor study processes and data collection after the first cohort has been processed. The Research Teams may also undertake spot checks for monitoring purposes at any point throughout the entire study, as issues regarding poor data quality, deviation of the protocol and GCP will raise extra monitoring visits.

At the end of the study, a final monitoring session from the Research team will be undertaken to assess the conduct of the study and ensure good quality data. The sites will be monitored under the trial risk assessment and monitoring plan.

Between each cohort, the CI will discuss the performance of the Investigation Team and the cohort participants informally with the PI and the Investigation team to identify any practical and/or logistical difficulties during the cohort which may be improved for future cohorts or used to improve study design for future research projects. This will also be fed back to the Oversight Committee.

Trials staff will regularly contact the site research team to check on progress and address any queries they may have. Trials staff will check incoming ICFs and CRFs for compliance with the protocol, data consistency, missing data and timing. Sites will be sent DCFs requesting missing data or clarification of inconsistencies or discrepancies. Sites will be requested to send copies of signed consent forms and other documentation for in-house review for all participants providing explicit consent. This will be detailed in the monitoring plan.

13.5 Audit and Inspection

The CI will allow monitoring, audits, ethical review, and regulatory inspections to take place at clinical trial site. This means that direct access to source data and documents will be provided. The CI will fully comply with these visits and any necessary follow-up. Additionally, sites are requested to notify the sponsor of any relevant inspections.

By allowing these measures to take place, we can ensure the highest level of quality and safety for the trial. This will ultimately lead to better outcomes for the patients involved and help advance medical knowledge.

13.6 Medical Device Recall

The Sponsor is responsible for product recall.

The actions below shall be taken should a recall of the Salurate Sampling System be required;

- The Sponsor shall start an investigation with the CI supporting, to identify the route of the issue and the affected batch
- The sponsor shall immediately notify the MHRA regarding Field Safety Corrective Actions that will be carried out, and request MHRA advice
- The CI must inform the clinical trial team of all the sites involved in the study
- Depending on the recall class, as dictated by the MHRA (1-3), batches or the entire sampling inventory may be recalled.
- The CI shall confirm if the affected batch is in stock; if yes, it should be immediately quarantined until the Sponsor authorises either;
 - The release of the batch,
 - Return to the Sponsor/manufacturer
 - Destruction of the batch
- The PI or CI must identify participants with access to the affected batch for the information to be available when necessary. This task can be delegated to other members of the clinical team.
- A draft of the Field Safety Notice (FSN) must be shared with the MHRA for comments before an official FSN is released
- An FSN shall be submitted to the MORE Portal, and the recall initiated
- New stock will be ordered by the CI

13.7 Notification of Serious Breaches

It is imperative to promptly document any deviation from the Protocol in the HR-P-52 *Protocol Deviation Log.* This log will be shared with the Sponsor after each cohort. It is the Sponsor's responsibility to inform the licensing authority in writing within seven days of discovering any significant relating to the trial. Any deviation that may impact the physical and mental safety of participants or staff, or have an effect on the quality or integrity of the data, and subsequently the scientific value of the trial, must be treated with utmost seriousness. Serious breaches, they must be immediately recorded in the Protocol Deviation Log and reported to the Sponsor.

Promptly reporting any suspected trial-related serious breach of GCP and/or the trial protocol is mandatory and Trials office shall be informed. Where the Trials Office is investigating whether or not a serious breach has occurred, sites are also requested to cooperate with the Trials Office in providing sufficient information to report the breach to the MHRA where required and in undertaking any corrective and/or preventive action.

Sites that exhibit serious and persistent non-compliance with the protocol and/or GCP and/or poor recruitment may be suspended from further recruitment. Any major problems identified during monitoring must be reported to the Trial Management Group, Trial Steering Committee, the site's R&D Department, and the REC. Serious breaches of GCP and/or the trial protocol also must be reported to the REC and MHRA. When reporting to the REC and/or relevant regulatory bodies, a copy of the documentation relating to serious breaches will equally be sent to the sponsor.

14 END OF STUDY DEFINITION

The end of the study will be the point at which 4000 complete datasets have been received. REC and MHRA will be notified within 90 days of the trial ending.

15 STATISTICAL CONSIDERATIONS

A cohort of 4,000 participant mothers would experience an estimated 460 events overall (PE/PIH/ IUGR) assuming a prevalence of 11.5%, and 100 cases of IUGR (the least prevalent of the conditions being studied), assuming a prevalence of 2.5%, based on observations from the Denmark study. This sized cohort would allow sensitivity of the Salurate algorithm to identify IUGR to be estimated with a 2-sided 95% confidence interval (CI) to within plus or minus 10% of the point estimate (if sensitivity was actually 50%, i.e. 95% CI 40% - 60%) and this would improve to a more precise confidence interval to within plus or minus 6% of the point estimate if the sensitivity proved to be around 90% (i.e. 95% CI 84% - 96%).

Additionally, a cohort of N=4,000 would allow sensitivity of the Salurate algorithm to identify any of the events of interest (prevalence 11.5%) to be estimated with greater precision, with a 2-sided 95% confidence interval to within plus or minus 5% of the point estimate (if sensitivity was actually 50%, i.e. 95% CI 45% - 55%) and this would improve to a more precise confidence interval to within plus or minus 3% of the point estimate if the sensitivity proved to be around 90% (i.e. 95% CI 87% - 93%). Specificity will be estimated to a much higher degree of precision because the majority of participants/babies in the cohort will not encounter adverse outcomes, and so they will comprise the much larger sample.

All analysis will be conducted by the study statistician Professor [name], using StataSE v16.1 statistical analysis software.

The Salurate study is quantitative research (numerical outcome). The quantitative data for this study will be analysed and reported according to the relevant reporting guidelines (STARD, BMJ. 2015;351:h5527. PMID: 26511519 and TRIPOD BMJ 2015; 350:g7594. PMID: 25569120).

All clinical primary and secondary outcomes (maternal and neonatal) will be presented across the whole cohort as percentages with 95% confidence intervals, missing outcomes data will be presented. Women's characteristics at enrolment into the study will also be presented with percentages or summary statistics as appropriate. Salivary uric acid concentration (Salurate) observations will be presented graphically over time from the initial 10-14 week pregnancy record through to the end of study participation i) for the whole cohort, ii) by primary outcome (HDP present or absent), iii) for each secondary outcome, including adverse maternal or perinatal outcomes.

Numbers and percentages of missing Salurate reports will be presented by week of pregnancy with the number of women participating in the study as the denominator (which may vary in the last weeks of the study depending on when they give birth). This will be used to assess the degree of compliance of women to the testing regime. No multiple imputation or other forms of missing data replacement will be used to estimate missing values of Salurate. No missing data replacement will be employed for clinical outcomes or participant's characteristics at enrolment, and every effort will be made to record these data. We anticipate that rates of data missingness will be low.

Multilevel Logistic/Linear regression models, as appropriate, will be used to determine the relationship between Salurate results and the primary and secondary outcomes in this cohort. The Salurate algorithm will be employed and its sensitivity, specificity, positive predictive value (PPV) and negative predictive value (NPV) to identify the primary outcome will be presented with 95% confidence intervals. We will also determine how soon the primary outcome would be indicated using Salurate results and compare this with traditional prediction methods using standard NHS monitoring data.Subgroup analyses will explore whether the Salurate algorithm has greater diagnostic value in particular women according to baseline characteristics, although these analyses may not have enough statistical power to be definitive. Adverse Event and Serious Adverse Events details will be listed.

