5.2 Primary Objective

a) To test the hypothesis that the inclusion of the Salurate pregnancy remote self-monitoring system in a pregnant woman's care pathway would predict the subsequent development of HDP prior to is currently possible using traditional methods.

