5.3 Secondary Objectives

- a) To assess whether Salurate could detect occurrence of other important placentally-mediated outcomes such as fetal growth restriction (FGR) spontaneous preterm birth (sPTB), stillbirth and GDM.
- b) To assess the cost effectiveness of Salurate testing compared to current care methods.
- c) To assess the degree of compliance of pregnant women to a self-sampling weekly Salurate test regimen.
- d) To assess the algorithm efficacy in a demographically diverse population.

Note: the current care methods to diagnose HDP involve assessing blood pressure, proteinuria (diagnosed via urinalysis/24 hour collection), blood test results and/ or PIGF levels.

6 Salurate System

Salurate is a non-invasive, home-use self-sampling system.

A weekly saliva sample is taken in the morning before eating, drinking, or brushing teeth. This sample is applied to a colorimetric test paper (test cartridge). An enzymatic reaction occurs, which producing a purple colour of varying intensities. The intensity of colour change is directly proportional to SUA concentration.

Figure 1. Uric acid linearity and colour intensity

A custom developed smartphone app, used in conjunction with a cloud server, receives the image from the smartphone app and extracts the relevant data. This data is combined with previous weeks' data and presented to the prediction algorithm.

The prediction algorithm is designed to detect patterns in the data that identify whether a hypertensive event is likely to occur in the pregnancy.

Figure 2. Salurate System Overview

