10 SCHEDULE OF EVENTS

10.1 Preparation

MIAT and its subcontractors will secure components, materials, and will assemble approximately 5000 Salurate test kits, each containing sufficient components to submit 30 samples. Each kit will be issued with a unique Kit ID number, which in turn will be linked to a batch number for traceability purposes.

These kits will be dispatched to recruiting locations in pre-agreed quantities, and will be refrigerated upon arrival².

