10.5 Data collection; Salurate Testing, Week 12 – Conclusion of pregnancy

Each participant submits weekly samples from enrolment \leq 16 weeks of gestation until conclusion of pregnancy.

Should a test kit be destroyed or otherwise misplaced during the study, replacement kits will be issued and Kit ID information updated accordingly.

² Subject to resources available at each facility, MIAT may supply refrigeration equipment to ensure preservation of product

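### Nothing in the protocol keeps alarms raised on or after diagnosis out of the accuracy measures, and no date of HDP diagnosis is named for collection

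*Protocol*

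**What the plan says.** - **Objective (Protocol 5.2).** Including Salurate in the care pathway "would predict the subsequent development of HDP prior to is currently possible using traditional methods".
- **Sampling (Protocol 10.5).** Each woman samples weekly from enrolment, at up to 16 "weeks of gestation until conclusion of pregnancy". No stop at diagnosis is stated. Kits are made up in Section 10.1, "each containing sufficient components to submit 30 samples".
- **Algorithm (Protocol section 6).** After each image is read, "This data is combined with previous weeks' data and presented to the prediction algorithm". A woman is therefore assessed repeatedly on accumulating data.
- **Accuracy (Protocol 15).** The planned measures are set out thus: "The Salurate algorithm will be employed and its sensitivity, specificity, positive predictive value (PPV) and negative predictive value (NPV) to identify the primary outcome". Each gets a 95% confidence interval. No index sample, landmark week, lead time or cut at diagnosis is named.
- **Timing (Protocol 15).** The next sentence plans a separate comparison of how early Salurate and standard NHS monitoring would indicate the outcome.
- **Outcome data (Protocol 12).** The CRF is described as holding the presence or absence of each HDP end-point. Sections 10.4 and 10.6 name no date of diagnosis.
- **Regression (Protocol 15).** "Multilevel Logistic/Linear regression models, as appropriate, will be used to determine the relationship between Salurate results and the primary and secondary outcomes". Neither the levels nor the dependent variable is named.

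**The concern.** A test can only predict from information available before the event. If samples taken on or after diagnosis may supply the alarm, a marker that rises once disease is clinically present scores true positives. The accuracy table then mixes prediction with detection, and sensitivity no longer answers the primary objective.

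Two related matters follow. If any weekly alarm makes a woman positive, false alarms accumulate, and women who deliver early have fewer looks than those who reach term, so specificity and PPV depend on how long women were sampled. And the remedy needs a diagnosis date: if it is not collected while the study runs, a later analysis plan may be unable to apply a cut, particularly as Section 12 has the register linking identity to Study ID destroyed on completion.

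**Working it through.** **1. The plan's own figures.** Section 15 expects 4,000 × 0.115 = 460 events and 4,000 × 0.025 = 100 cases of IUGR. The half-width is 1.96 × √(p(1−p)/n):

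| Cases | Sensitivity | Computed | Stated |
|---|---|---|---|
| 100 | 50% | 9.8% | 10% |
| 100 | 90% | 5.9% | 6% |
| 460 | 50% | 4.6% | 5% |
| 460 | 90% | 2.7% | 3% |

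All reproduce. They treat each woman as one binary result, and that single result is what Section 15 does not define.

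**2. Effect of the missing cut.** The protocol gives no alarm rates, so these inputs are assumptions: weekly samples from week 12; diagnosis at 30 to 39 weeks, evenly spread; delivery 0 to 5 weeks later, capped at week 41; weekly false-alarm rate f of 0.5% or 1%; true signal q of 20% or 40% per week, present from the sample two weeks before diagnosis; independent weeks; any alarm counts. With k samples in the window, j of them in the signal period, sensitivity = 1 − (1−f)^k × (1−q)^j.

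One case by hand, with diagnosis at week 35, delivery at week 37, f = 0.5% and q = 20%:
- no cut (weeks 12–37, k = 26, j = 5): 1 − 0.878 × 0.328 = 71%
- before diagnosis only (weeks 12–34, k = 23, j = 2): 1 − 0.891 × 0.640 = 43%
- at least 2 weeks ahead (weeks 12–33, k = 22, j = 1): 1 − 0.896 × 0.800 = 28%

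Averaged over all diagnosis and delivery weeks:

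| f | q | No cut | Before diagnosis | ≥2 weeks ahead |
|---|---|---|---|---|
| 0.5% | 20% | 71.5% | 42.8% | 28.2% |
| 1% | 20% | 74.9% | 48.9% | 35.5% |
| 0.5% | 40% | 92.1% | 67.8% | 46.1% |
| 1% | 40% | 93.1% | 71.3% | 51.6% |

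**3. A check free of the timing assumptions.** If true pre-diagnosis sensitivity is s, and m samples on or after diagnosis each alarm with probability a, the observed value is s + (1−s)(1 − (1−a)^m). With s = 50% and m = 3 this gives 52.9% (a = 0.02), 63.5% (0.1), 82.9% (0.3) and 93.8% (0.5). The inflation is small only if the test rarely alarms after diagnosis.

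**4. Repeated looks in women without HDP.** If any alarm counts and weeks are independent, the proportion ever alarmed is 1 − (1−f)^28: 25% at f = 1%, 43% at 2%, 76% at 5%.

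**5. Multilevel model (subordinate).** HDP takes one value per pregnancy. In one simulated data set of 800 women with 26 weekly rows each and 11.5% with the outcome, a random-intercept logistic model with HDP as the response had a log-likelihood rising from −2249 at a random-effect SD of 1 to −583 at 5, −351 at 20 and −318 at 40. There was no interior maximum in that range.

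**The case against.** **The protocol is silent.** A reader might infer that it counts alarms after diagnosis as predictions. It does not say so. Which samples enter the accuracy table is often left to an analysis plan, and one may exist. That limits the claim to what the text fails to exclude. It does not remove the point, because the objective, the sampling window and the accuracy analysis do not fit together as written, and the cut needs a date that the protocol does not name. The CRF itself is not shown and may hold that date.

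**Timing is already planned.** The comparison of how early each method indicates the outcome should expose a test that gives no lead. That is fair, but it is not tied to sensitivity, specificity, PPV or NPV, and it needs the same diagnosis date.

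**The illustrations rest on assumptions.** Outputs built on accumulating data are correlated, so the 28-look figures are probably too high, and an any-alarm rule is not stated. A reader might also infer that sensitivity two weeks ahead falls below the false-positive rate. That occurs only if the signal starts one week before diagnosis: sensitivity at a two-week lead is then pure false alarm, 1 − 0.995^21 = 10% to 1 − 0.99^21 = 19%, against 14% to 25% over 29 looks in women without HDP. With the signal starting two weeks before, the lead-time figure exceeds the matching false-positive rate in every scenario. Part of the gap between the first and last columns also comes from the chosen lead, so the effect of the cut alone is the step from the first to the second.

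**The regression wording is open.** It allows a linear model with salivary uric acid as the response, which is workable. The degeneracy arises only if weekly rows repeat HDP as the response.

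**Conclusion.** The point holds as a gap between objective and analysis. Sampling continues to the end of pregnancy, the algorithm keeps receiving data, and nothing in Section 15 restricts a true positive to an alarm before diagnosis. Under the assumed rates the missing cut alone raises sensitivity from 43–71% to 71–93%; requiring two weeks' lead would leave 28–52%. These figures show the scale of the problem and do not forecast the study's result. The true size depends on alarm rates around diagnosis and on the time from diagnosis to delivery, none of which the protocol gives.

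The documents do not support two further readings: that the stated precision is wrong (it reproduces, and a cut at diagnosis alone leaves the number of cases unchanged), or that the multilevel model is certain to fail. The latter is a conditional point about which variable is the response.

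**What to change.** 1. Record the date of HDP diagnosis on the CRF, or confirm that the CRF already holds it, and say so where Section 12 describes the outcome data.
2. In Section 15, define one classification per woman using only samples dated before diagnosis. Fix the minimum lead in advance, for example 2 weeks with 4 weeks as a second analysis.
3. Alongside or instead, report accuracy at fixed gestational landmarks, for example 20, 24, 28, 32 and 36 weeks, among women still pregnant and undiagnosed, with HDP diagnosed after the landmark as the outcome. This also gives cases and non-cases the same sampling window.
4. Name the levels and response of the regression models. With HDP as the response, use landmark logistic or discrete-time hazard models rather than a weeks-within-woman random intercept. Keep the multilevel linear model for salivary uric acid as the response.

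The cost is Section 15 wording, modest programming and one CRF date. Reported sensitivity will be lower, and late landmarks will have fewer cases and wider intervals than Section 15 quotes. The date is best settled before outcome data accumulate, since it may be hard to recover once the linkage register is destroyed.
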